#### BENEFITS:

Potential benefits for all participants include free treatment with the potential to increase the likelihood of smoking cessation, which could in turn prevent smoking related morbidity and mortality as well as improve the effectiveness of psychiatric medications. All participants will be offered the nicotine patch, an FDA-approved tobacco cessation pharmacotherapy, for free. By participating in the research, all participants will also benefit from knowing they may ultimately be helping others as they will have helped us test an intervention. The costs of participating in the research will be minimized through our extensive efforts to maintain confidentiality, reduce discomfort or distress, and minimize medical complications. Overall, it is expected that the potential benefits to participants in the proposed study will outweigh potential risks.

#### RISKS:

Nicotine patch side effects: All subjects who are ready to quit have no contraindications to the patch will be offered an 8-week supply of free nicotine patches. The nicotine patch has been in clinical use for almost 20

years. It is available over the counter and has been judged to be generally safe and efficacious with very few contraindications. If the participant has a medical contraindication to the nicotine patch (e.g., recent history of MI) he or she must obtain clearance from a medical provider in order to receive the patch from the study team (e.g., their PHP psychiatrist or their primary care provider). Initial dosing will follow package instructions. Study counselors will explain the patch's purpose, application, and side effects. Common side effects of the patch include local skin irritation at the site of the patch, nausea if the dose is too large or if the participant continues to smoke at a high level while using the patch, and disturbed and vivid dreams. Less common reactions include allergic reactions. A comprehensive meta-analysis of 129 studies involving 177,390 individuals concluded that there was no significant difference between Nicotine Replacement Therapy and placebo in prevalence of severe adverse events (SAEs) including suicidal ideation, heart attack, and mortality. Thus, the principal investigator of this study, [name]. expects the risk of using the nicotine patch in the current study be very minor. We will obtain a release to inform participants' psychiatric and primary care providers that they have enrolled in a tobacco cessation study and may have been started on the nicotine patch. Participants can call the study PI or their medical provider for information on managing side effects of the nicotine patch.

Nicotine Withdrawal Symptoms After Quitting: There is a strong likelihood that most study participants who quit smoking will experience some nicotine withdrawal symptoms, including anxiety, restlessness, anger, irritability, sadness, problems concentrating, appetite change and weight gain, insomnia, and decreased heart rate. Generally, these reactions are temporary and pose no serious health risks.

Worsening of psychiatric symptoms and emergent suicidality. Available evidence suggests that quitting smoking has not been associated with increases in psychiatric symptoms among those with mental illness and may even result in improvement in psychiatric symptoms. However, this population is at high risk for additional acute psychiatric episodes.

Need for adjustment of psychiatric medication following cessation: Cessation in some patients on psychiatric medications (most notably antipsychotics, benzodiazepines, SSRIs, SNRIs and tricyclic antidepressants) can produce increased serum drug levels. Medication doses will need to be monitored upon cessation to maintain the proper therapeutic dose.

Confidentiality or loss of privacy. We will collect potentially sensitive information about participants; if released inappropriately, participants may experience embarrassment or distress. The seriousness of the consequences would depend on the nature of the information revealed and to whom the information was revealed. Given the numerous steps we take to protect participant confidentiality, we think the risk of a breach of confidentiality is low.

Discomfort or distress when completing assessment and treatment procedures. Some participants may feel uncomfortable or distressed answering personal or private questions during assessment or treatment. In our previous studies, when individuals do report discomfort in these situations, it is mild. Participants will be informed at the beginning of each assessment that their participation is voluntary and they may refuse to answer any questions that make them uncomfortable or withdraw from the study at any time.

## 1. ADEQUACY OF PROTECTION AGAINST RISK

### Recruitment and Informed Consent

Participants who appear to meet inclusion/exclusion criteria, will be informed about the study by partial hospital program research assistants. If they express interest, they will be screened for eligibility criteria by the research assistants. At first contact, all participants will first be given a brief verbal overview of the study. If participants agree to be screened and pass the screening questions based on inclusion/exclusion criteria they will be invited to participate, and will complete a contact information form. The participant will then be scheduled for a baseline assessment visit and counseling session. Written informed consent (including a description of the nature, purpose, risks, and benefits of the study) will be obtained from participants before initiating the baseline assessment. The voluntary nature of the study and the participant's right to withdrawal at any time will be stressed during the consent process; this information will be provided to participants in written form at the time of consent. As part of the consent process, to ensure comprehension, following the participant reading the consent form, we will verbally explain the study to the participant. All participant questions will be answered prior to obtaining written consent. Research assistants and study counselors will obtain consent.

### PROTECTION AGAINST RISK:

Minimization of nicotine patch side effects: The nicotine patch is an over the counter medication with few serious side effects. However, participants will be screened for all contraindications to the patch. If a contraindication is present, they must obtain approval from a medical provider before participating. Participants will agree to consult with their outpatient medical providers regarding the safety of using the patch if their medical status changes after the patch is initially provided. Further, study counselors will explain the patch's purpose, application, and side effects, as well as how to use the patch in a manner that minimizes risk.

To minimize skin reactions, participants will be instructed to move the site of patch placement each day and to not repeat site use for at least one week. Patch dose may be adjusted downward if there is significant nausea or other reactions. Participants will be instructed to remove the patch before bed if it significantly interferes with sleep. Participants with severe side effects will be asked to discontinue patch use and contact their primary care provider before resuming.

Minimization of nicotine withdrawal symptoms after quitting: Participants that decide to use the nicotine patch will be told that it will reduce but not entirely eliminate withdrawal symptoms. Participants will be instructed to call their outpatient physician or psychiatrist in the case of severe withdrawal reactions. Withdrawal symptoms typically abate within 1 to 2 weeks of quitting and are not medically dangerous.

Minimization of risk from worsening of depression and emergent suicidality: There is no evidence indicating that participation in this trial will worsen depression or cause suicidality. In fact, other studies have found that quitting smoking is associated with improvements in psychiatric symptoms. However, given that participants will be enrolled during an acute psychiatric episode, it is likely that some participants will experience worsening of depression during this study. A minority may experience episodes of suicidal ideation. Thus, we will monitor and respond to these issues in an ethically sensitive manner.

As part of the Partial Hospital program, all patients are referred to a psychiatrist and a therapist upon discharge. We will obtain a release to inform these mental health providers that their patient is attempting to quit smoking and could experience symptom exacerbation. Participants will be informed that, in the case of symptom exacerbation, they should: (1) discuss the symptoms with their psychiatrist, therapist and/or primary care provider, (2) page [name], a licensed psychologist ([name], a licensed psychologist, will cover if [name] is not available); or, if they pose an immediate risk to themselves or someone else, (3) call 911 or present to the nearest emergency room.

If a participant reports active suicidality (i.e., any recent suicidal attempts, suicidal gestures, or self-injurious behavior; any current plan or intent to engage in suicidal or self-injurious behavior) to any study staff at any time, the participant will be assessed by [name] or [name], who will respond in an appropriate and ethical manner according to the standards of care for suicide prevention (e.g., referral to immediate emergency psychiatric care if danger to self is imminent).

Minimization of risk of inappropriate psychiatric medication dose upon cessation: Upon enrollment in the study, we will inform the patient's PHP psychiatrist of the patient's planned cessation attempt. A benefit of stopping smoking while in the PHP is that patients meet with their psychiatrists daily while in the program to monitor medication effects and side effects. In addition, we will obtain a release of information from the patients to their outpatient psychiatric provider and primary care provider. Upon enrollment, we will fax these providers a form letter indicating that the patient plans to attempt to stop smoking, their anticipated quit date, that they will be using the nicotine patch, and information on potential medication interactions with tobacco cessation.

Minimization of loss of confidentiality/privacy: All data and records will be safeguarded according to the strict privacy/confidentiality policies of The Miriam Hospital Institutional Review Board (IRB). Confidentiality will be maintained by numerically coding all data, disguising identifying information, and keeping data in secure electronic locations or locked in file drawers. All electronic data will be numerically coded and stored on a limited access server in a secure research space. All paper forms will be stored in locked file cabinets in a locked room. Names of participants will be stored separately. Participant information will be accessible only to research staff, who are pledged to confidentiality and complete training in the ethical conduct of research (i.e., both HIPAA and CITI trainings). [name] will also personally train staff on maintenance of participant confidentiality. Identifying information will not be reported in any publication.

Minimization of discomfort or distress when completing assessment and treatment procedures: We will take three specific steps to reduce the possibility of discomfort or distress:

*Study will be clearly explained.* A detailed explanation of the study, including what study participation would involve, the nature of the questions participants will be asked to answer, the nature of measurements, the

nature of the intervention being tested, and the right to withdraw from the study at any time without penalty, will be provided to the participants, both verbally and in writing (through the informed consent form). Participants will be encouraged to ask questions about the study. Individuals who are uncomfortable answering these types of questions, assessments, or interventions likely will not choose to participate. Those who choose to participate but are very uncomfortable with the questions, assessments or interventions will be told that they can refuse these assessments or choose to withdrawal from the study.

*Private setting.* To help ensure clients' comfort, they will answer survey questions in a private setting. Thus, they should not be concerned that another individual would be able to observe these assessments.

*Staff Training.* All staff interacting with participants will be trained by [name] to ask questions and complete assessments in a sensitive manner and be supportive to any participant experiencing discomfort or distress.

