## PROCEDURES:

Recruitment. Participants will be recruited during PHP treatment. As standard clinical care, all patients are screened for smoking status upon admission. Current daily smokers will be informed about the study at that time and invited to be screened for participation. All women of childbearing potential who would like the nicotine patch will complete a pregnancy test prior to inclusion into the study. Eligible and interested participants will complete an enrollment/pre-quit visit while enrolled in the PHP, which includes a baseline assessment, random assignment to a condition, the first counseling session and 4 weeks of nicotine patches (to be started on the quit day). The enrollment visit can be on the same day as the first pre-quit visit counseling but doesn't need to be. Participants will then complete a second pre-quit counseling session (within one week of the pre-quit session but before discharge). If the participant is to be discharged before their first or second counseling session, the counselor will choose one of the following options in order of preference ((1) complete the second counseling session early but not on the same day as the first counseling session,(2) have the patient return to the partial hospital program location for the first or second counseling session, (3) complete the counseling session by phone and mail materials distributed during the counseling session). Following the second counseling session, participants will continue in their assigned post-discharge intervention consisting of up to 5 Quitline or ACT telephone sessions.

Study outcomes will be assessed at the end of the counseling treatment at an in-person visit 5 weeks after their visit 2 date OR 24 hours after the last counseling session by a research staff member, whichever is later. As an incentive for completion of the follow-up assessment, those in either group who complete this visit will receive \$20 compensation and an additional 4 weeks of the nicotine patch. We will try to schedule visits around existing appointments in the hospital system to increase compliance.

Randomization will use block randomization, unknown to the counselor or the participant. In order to balance any benefit of bupropion treatment in combination with the nicotine patch across treatment conditions, randomization will be stratified by bupropion use.

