## Interventions.

Nicotine patch. All participants will receive usual psychiatric care plus an offer of the nicotine patch (up to 8 weeks), dosed per package instructions. At the second pre-quit session, participants will be instructed on patch use. The first 4 weeks of patch will be distributed at enrollment and the second 4 weeks will be distributed at the follow-up visit.

Enhanced Usual Care (EUC). Participants in the EUC condition will receive one in-person counseling sessions during the PHP and a second telephone session the week following: the first session will occur prior to the quit day and will focus on establishing a quit plan and instructing the participant on the use of the nicotine patch; the second session will occur prior to quit day and will assess for any difficulties using the nicotine patch. After the second session, participants will be electronically referred to the RI state quitline. This quitline offers an enrollment call and 5 proactive counseling telephone counseling telephone calls to those who enroll. Quitline staff make up to 3 attempts per call to reach users. Total scheduled counseling time offered is 120 minutes. If the participant is unexpectedly discharged before their first counseling visit, the counselor will choose one of the following options in order of preference ((1) complete the second counseling session early but not on the same day as the first counseling session,(2) have the patient return to the partial hospital program location for the first counseling session, (3) complete the counseling session by phone and mail materials distributed during the counseling session).

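### The schedule does not place quit day inside the partial hospital stay, so it is undefined who gets the daily psychiatrist contact cited for medication monitoring, and the provider letter can misstate quit date and patch use

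*Protocol*

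**What the plan says.** The Risks section of the Protocol warns that stopping smoking can raise blood levels of several classes of psychiatric drug, and adds: "Medication doses will need to be monitored upon cessation to maintain the proper therapeutic dose".

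The medication-dose paragraph under Protection Against Risk responds with several items:
- Notice to the treating psychiatrist in the partial hospital program (PHP): "Upon enrollment in the study, we will inform the patient's PHP psychiatrist of the patient's planned cessation attempt".
- Daily contact: "A benefit of stopping smoking while in the PHP is that patients meet with their psychiatrists daily", for the purpose of watching medication effects and side effects.
- A release, and a form letter faxed at enrollment to the outpatient psychiatric and primary care providers. It covers the plan to quit, "their anticipated quit date, that they will be using the nicotine patch", and information on interactions.

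The same section says that every patient is referred to outpatient mental health care on leaving, and tells participants whom to contact if symptoms worsen.

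On timing, Procedures describes a "second pre-quit counseling session (within one week of the pre-quit session but before discharge". If discharge comes first, the fallback is an early second session, a return visit, or a telephone session. Interventions describes the second contact in enhanced usual care (EUC) as "a second telephone session the week following" and says that "the second session will occur prior to quit day". In the ACT arm it lists one in-person contact and six by telephone.

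**The concern.** The risk begins when the patient stops smoking. Daily psychiatrist contact is the only item in the medication-dose paragraph that amounts to monitoring, since the others inform providers. It is offered on the premise that the patient quits during the PHP, and the schedule does not make that so.

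After discharge, the letter is one of the items that tells the prescriber when to watch for a change in drug levels. If it carries a date set before the quit plan, or reports a patch the patient declined, the prescriber is working from wrong information. The stake is a safety statement whose coverage cannot be determined. The analysis of the trial is not affected.

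**Working it through.** The plan gives no figure to reproduce, so the check has three parts.

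**1. Order of events.** Procedures calls both early sessions pre-quit for all participants. The nicotine patch paragraph in Interventions, which also covers everyone, speaks of a second pre-quit session. The EUC paragraph puts session 2 before quit day explicitly. Quit day therefore follows session 2.

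| Source | Session 2 | Quit day relative to discharge |
|---|---|---|
| Procedures, default | Within a week of session 1, before discharge | Not stated |
| Procedures, fallback by return visit or telephone | After discharge | After discharge, if the schedule is followed |
| Interventions, EUC | By telephone, the following week | Not stated |
| Interventions, ACT arm | By telephone, no timing given | Not stated |
| Protection Against Risk | Not stated | Presumes quitting during the PHP |

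The second row needs no assumption: if a pre-quit session happens after discharge, so does quit day, and days of PHP contact after quitting are zero.

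**2. How much contact the default schedule could give.** Count PHP days from quit day onward as

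max(0, R − (s + g) + 1)

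- R: PHP days left after session 1. Assumed, because the documents give no length of stay.
- s: days from session 1 to session 2. Taken as 1 to 7, from Procedures.
- g: days from session 2 to quit day. Assumed, because the documents set none.

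Days are counted consecutively, ignoring weekends. For example, R = 10, s = 7, g = 1 gives 10 − 8 + 1 = 3, and s = 1 gives 10 − 2 + 1 = 9.

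| R | g = 1 | g = 3 | g = 7 |
|---|---|---|---|
| 3 | 0–2 | 0 | 0 |
| 5 | 0–4 | 0–2 | 0 |
| 7 | 0–6 | 0–4 | 0 |
| 10 | 3–9 | 1–7 | 0–3 |
| 14 | 7–13 | 5–11 | 1–7 |

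Coverage runs from nothing to 13 days over these inputs, and the documents do not select a row or a column.

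**3. The letter.** It is faxed at enrollment. In EUC the quit plan is made in session 1, which Procedures allows on a later day than enrollment, so the quit date in the letter can precede the plan. The letter also says the patient will be using the patch. Yet the exclusion criteria, Interventions and Protection Against Risk all treat the patch as the participant's choice, and the Risks section describes notice to providers only in conditional terms. For anyone who declines the patch, the letter is wrong. No update is described.

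**The case against.** The strongest reply is that a gap has been found and no failure shown. Procedures places session 2 before discharge without saying how long before, and with a long enough stay a participant could have more than a week of daily contact after quitting. A telephone session does not show that the patient has left, because the PHP is a day program and patients go home at night. The name given to the later telephone phase, post-discharge intervention, does not date quit day. Daily contact is presented as one benefit among several, beside the provider notices, the release, the discharge referral and the instructions on worsening symptoms. The quit date in the letter is openly labelled as anticipated.

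Most of this stands. A reader might infer that the schedule puts quit day at or after discharge, so that the safeguard is largely absent or nearly everyone quits without daily contact. The documents do not support that, because they give neither a length of stay nor a rule tying quit day to discharge. A reader might also infer that the Aim 1 safety assessment is undermined. It is not: the SAP speaks of the safety of offering an intervention during a PHP and counts rehospitalization over the whole treatment period, which does not depend on where quitting occurs.

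The reply does not remove the conflict over session 2, the zero coverage for participants on the post-discharge fallback, or the letter's statement about an optional patch. The other protections do reach past discharge, but they inform providers and patients and specify no dose monitoring.

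**Conclusion.** The point holds as an unsecured premise and a letter that can be inaccurate. Four things follow from the text alone:
- Procedures and the EUC paragraph disagree on how and when session 2 takes place.
- No section places quit day relative to discharge.
- Participants whose pre-quit sessions fall after discharge, and who follow the schedule, cannot have daily PHP contact after quitting.
- The letter is wrong for those who decline the patch, and its quit date may precede the quit plan.

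For everyone else, daily contact after quitting may or may not exist. The 0 to 13 days above rests on assumed stays of 3 to 14 days after session 1 and assumed gaps of 1 to 7 days to quit day. It shows that the answer is open and does not estimate the share affected. The correction should be made because it is cheap and improves safety communication.

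**What to change.** 1. Reconcile Procedures, the EUC and ACT paragraphs of Interventions, and the medication-dose paragraph of Protection Against Risk on two matters: how and when session 2 is held, and where quit day falls relative to discharge.
2. State in Protection Against Risk to which participants the daily-contact statement applies. What monitoring applies to the others is for the clinical team to decide.
3. Send, or re-send, the existing form letter once the quit date and the patch choice are known, and make its patch statement match that choice.
4. Record quit date and discharge date, neither of which is in the table of measures, and report how many participants quit before and after discharge. A count is enough. With 20 per group, splitting rehospitalization or distress scores by this post-randomization event would give cells too small to interpret.

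The cost is protocol wording, some letters sent twice, and two dates for each of 40 participants.
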